6. SYNOPSIS

Study Title: A Multicenter, Open Label Pilot Study to Explore the Efficacy and Safety of Acthar® in Subjects With Severe Noninfectious Intermediate Uveitis, Posterior Uveitis, or Panuveitis	
Protocol MNK61074105	Type: Phase 4
Condition/Disease:	Severe Noninfectious Intermediate Uveitis, Posterior Uveitis, or Panuveitis (NIPPU)
Approximate Number of Subjects: 30	Approximate Duration of Subject Participation: 48 weeks
Approximate Study Centers: 10 in the US	Approximate Duration of Study: 18 months
Design: This is a multicenter, multiple dose, open label study to examine the effects of Acthar in adult subjects with severe NIPPU. Approximately 30 subjects will be enrolled. Subjects with current severe NIPPU who meet entry criteria will be treated with Acthar 1 mL (80 units [U]) subcutaneously (SC) 2x/week for 36 weeks. Followed by a taper to Acthar 1 mL (80 U) SC once a week for 2 weeks, then 0.5 mL (40 U) SC once a week for 2 weeks. All subjects will have a follow-up contact 28 (\pm 14) days after their last dose of study drug.	
Objectives:	
Primary Objective	Endpoints
To explore the efficacy of Acthar in subjects with severe NIPPU in reducing aqueous and vitreous indicators of inflammation.	Proportion of subjects with a 2 or more step reduction from baseline (or achievement of Grade 0) in vitreous haze at 36 weeks. Proportion of subjects with a 2 or more step reduction from baseline (or achievement of Grade 0) in aqueous flare at 36 weeks. Proportion of subjects with a 2 or more step reduction from baseline (or achievement of Grade 0) in aqueous cells at 36 weeks.
Secondary Objective	Secondary Endpoints
To further explore the safety and tolerability of Acthar in subjects with severe NIPPU.	Incidence and severity of ocular adverse events (AEs). Incidence and severity of other AEs. New or worsening cataracts. Mean change in intra-ocular pressure (IOP).
Exploratory Objectives	Exploratory Endpoints
[REDACTED]	[REDACTED]

Study Title: A Multicenter, Open Label Pilot Study to Explore the Efficacy and Safety of Acthar® in Subjects With Severe Noninfectious Intermediate Uveitis, Posterior Uveitis, or Panuveitis	
Protocol MNK61074105	Type: Phase 4
Condition/Disease:	Severe Noninfectious Intermediate Uveitis, Posterior Uveitis, or Panuveitis (NIPPU)
[REDACTED]	[REDACTED]
Entry Criteria:	
Male or nonpregnant, nonlactating female subjects 18 years of age or older with who have been diagnosed with current severe NIPPU and have active disease at the Baseline Visit as defined by the presence of at least 1 of the following parameters in at least one eye despite at least 2 weeks of maintenance therapy with oral prednisone (or oral corticosteroid equivalent):	
Active, inflammatory, chorioretinal and/or inflammatory retinal vascular lesion.	
≥ 2+ anterior chamber cells (Standardization of Uveitis Nomenclature [SUN] criteria).	
≥ 1.5+ vitreous haze.	
Subjects must be willing to taper their current doses of corticosteroid and immunomodulatory therapy to the minimum effective dose during the study.	
Subjects may be under treatment with any immunosuppressants, immunomodulators, or biologic agents for a comorbid condition as long as they are on a stable dose for 2 weeks prior to screening. Subjects with proliferative or severe nonproliferative diabetic retinopathy, clinically significant macular edema due to diabetic retinopathy, neovascular/wet age-related macular degeneration, abnormality of vitreoretinal interface with the potential for macular structural damage independent of the inflammatory process or severe vitreous haze that precludes visualization of the fundus at the Baseline Visit will be excluded.	
Subjects with Type 1 or Type 2 diabetes mellitus, tuberculosis, history of hepatitis, peptic ulcer, active infection, or any contraindication for Acthar will be excluded.	

Study Title: A Multicenter, Open Label Pilot Study to Explore the Efficacy and Safety of Acthar® in Subjects With Severe Noninfectious Intermediate Uveitis, Posterior Uveitis, or Panuveitis	
Protocol MNK61074105	Type: Phase 4
Condition/Disease:	Severe Noninfectious Intermediate Uveitis, Posterior Uveitis, or Panuveitis (NIPPU)
Concomitant Medications and Treatments: Subjects are not permitted to receive live or live-attenuated vaccines; topical, ophthalmic, or intra-ocular corticosteroids for a concomitant condition during the study. The use of corticosteroid therapy and immunomodulators for uveitis are permitted provided the subject has been on a stable dose for at least 2 weeks prior to the Screening Visit and is willing to taper to the lowest effective dose during the study. Subjects with stable comorbid conditions that are commonly associated with uveitis may continue with their current therapies that were stable for 2 weeks prior to screening. All medications and nondrug therapies (eg, blood transfusions, oxygen supplementation) taken from 30 days prior to the Screening Visit and throughout the study will be recorded.	
Study Drug and Treatment Administration: Acthar is a sterile preparation of adrenocorticotrophic hormone (ACTH) analogue formulated in a gel for repository administration. Acthar is supplied as 5 mL multidose vials. Acthar vials contain 80 U of ACTH per mL. The following treatments will be administered to all subjects: Acthar 1 mL (80 U) SC doses 2x/week for 36 weeks, followed by a taper to 1 mL (80 U) SC doses once per week for 2 weeks and then 0.5 mL (40 U) SC once a week for an additional 2 weeks.	
Efficacy Evaluations: The following efficacy assessments will be evaluated: Ophthalmic Examination, Spectral domain optical coherence tomography (SD-OCT), Fundus Photography, Fluorescein Angiography, and T-cell numbers.	
Safety Evaluations: The following safety assessments will be evaluated: adverse events, ophthalmology examinations, physical examination, clinical laboratory test results (Chemistry, Hematology, lipid profile and Urinalysis), glycosylated hemoglobin (HbA1c), pregnancy testing, and vital signs.	
Quality of Life/ Health Outcome Evaluations: The following quality of life (QOL)/health outcome assessments will be evaluated: National Eye Institute Visual Function Questionnaire-25.	
Statistical Methods: Analysis Populations The Modified Intent-to-Treat (mITT) Population will include all subjects who receive at least 1 dose of study drug and who contribute any postbaseline efficacy data to the study. The Per-Protocol Population will include the subset of the mITT population who complete the study as per protocol, have no missing primary endpoint data, and do not have any major protocol deviations. The Safety Population will include all subjects who receive 1 or more doses of study drug.	

Study Title: A Multicenter, Open Label Pilot Study to Explore the Efficacy and Safety of Acthar® in Subjects With Severe Noninfectious Intermediate Uveitis, Posterior Uveitis, or Panuveitis	
Protocol MNK61074105	Type: Phase 4
Condition/Disease:	Severe Noninfectious Intermediate Uveitis, Posterior Uveitis, or Panuveitis (NIPPU)
Sample Size A total of 30 subjects will be enrolled in this study. No formal sample size calculations were performed. The sample size was determined empirically.	
Efficacy Analysis	
All efficacy analyses will be performed on the mITT population. Selected analyses will be performed on the Per-Protocol population.	
The primary efficacy endpoints will include:	
Proportion of subjects with a 2 or more step reduction from baseline (or achievement of Grade 0) in vitreous haze at 36 weeks.	
Proportion of subjects with a 2 or more step reduction from baseline (or achievement of Grade 0) in aqueous flare at 36 weeks.	
Proportion of subjects with a 2 or more step reduction from baseline (or achievement of Grade 0) in aqueous cells at 36 weeks.	
The primary efficacy endpoints will be analyzed on both mITT population and the Per-Protocol population. The endpoints will be summarized with frequency tables and evaluated with one-sample binomial test. The nominal p-values along with the 95% confidence intervals (CI) will be provided.	
For subjects with both eyes affected, the change from baseline will be determined based on the eye with the worst severity at baseline. If both eyes have the same severity at baseline, the right eye will be used to determine change from baseline. The same principle will be applied to efficacy endpoints when change from baseline is evaluated.	
Other efficacy endpoints will be summarized with descriptive statistics and the changes from baseline will be evaluated with test statistics and/or 95% CI as appropriate.	
Safety Analysis	
Treatment-emergent adverse events and serious adverse events will be summarized using the appropriate version of MedDRA by preferred term within system organ class.	
Other safety data will be listed and summarized descriptively or graphically, as appropriate.

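### Each primary responder rate includes subjects already at Grade 0 on that sign at baseline, so it mixes reduction with absence of the sign; flare is most exposed

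*Combined protocol and SAP*

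**What the plan says.** All references are to the Combined protocol and SAP, section 6 (Synopsis), which is the text available for this review.

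- **Primary endpoints.** There are three, identical in form. The one for flare is "Proportion of subjects with a 2 or more step reduction from baseline (or achievement of Grade 0) in aqueous flare at 36 weeks"; the other two put vitreous haze and aqueous cells in its place. The stated primary objective is to explore reduction of aqueous and vitreous signs of inflammation.
- **Entry Criteria.** Active disease is "defined by the presence of at least 1 of the following parameters in at least one eye". The first parameter is "Active, inflammatory, chorioretinal and/or inflammatory retinal vascular lesion". The other two are anterior chamber cells of at least 2+ and vitreous haze of at least 1.5+. Flare is not listed.
- **Analysis sets.** "The primary efficacy endpoints will be analyzed on both mITT population and the Per-Protocol population". The mITT set needs one dose and any postbaseline efficacy data. The Per-Protocol set adds completion, complete primary endpoint data and no major deviations. Neither sets a condition on the baseline grade of the sign.
- **Eye rule.** When both eyes are affected, "the change from baseline will be determined based on the eye with the worst severity at baseline", with the right eye used for ties. A further sentence extends this principle to efficacy endpoints that use change from baseline.
- **Background therapy.** Subjects must be willing to "taper their current doses of corticosteroid and immunomodulatory therapy to the minimum effective dose during the study".

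**The concern.** A responder rate meant to describe reduction should be taken over subjects who have something to reduce. Here one qualifying sign admits a subject to all three denominators. Someone who enters on a lesion alone may have no haze, cells or flare. Someone who enters on cells may have no haze, and the reverse. Cells and haze each have one entry route that guarantees a non-zero grade in at least one eye; flare has none. Calling flare the most exposed endpoint is a statement about the design, not about how often flare is absent.

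The Grade 0 alternative in the endpoint then matters. Taken literally, a subject at Grade 0 at baseline and at week 36 satisfies it, so absence of the sign is scored as response. If achieving Grade 0 implies a change, the same subject cannot respond but still counts in the denominator. The available text does not say which applies.

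With about 30 subjects and no control arm, these rates and their 95% confidence intervals are the main efficacy result. In an open-label study, an unstated scoring rule also leaves room to choose it after the data are seen.

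**Working it through.** **Inputs.** From the Synopsis: N = 30, chosen empirically; the three endpoint definitions; the entry rule; the two analysis sets. There is no power, expected rate or null proportion in the available text, so there is no figure of the plan's own to reproduce, and I compute no p-value. The following are assumptions:

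- z = share of subjects at Grade 0 on the sign at baseline
- s = share of those still at Grade 0 at week 36
- r = response rate among subjects who have the sign

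**Formulas.**

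- Literal reading: rate = (1 − z)r + zs. Difference from r = z(s − r).
- Change-required reading: rate = (1 − z)r. Difference from r = −zr.
- Gap between the two readings = zs, whatever r is.

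**Results with r = 30%.** For example, at z = 20% and s = 80%, the literal rate is 0.80 × 0.30 + 0.20 × 0.80 = 0.24 + 0.16 = 40%.

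| z | Literal, s = 100% | Literal, s = 80% | Literal, s = 60% | Change required |
|---|---|---|---|---|
| 5% | 33.5% | 32.5% | 31.5% | 28.5% |
| 20% | 44% | 40% | 36% | 24% |
| 50% | 65% | 55% | 45% | 15% |

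**Worked case for flare (assumed counts).** Of 30 subjects, 10 are at Grade 0 at baseline and 6 of the other 20 respond. Intervals are Clopper-Pearson 95%.

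| Scoring | Responders | Rate | 95% CI |
|---|---|---|---|
| Subjects with flare at baseline only | 6/20 | 30.0% | 11.9–54.3% |
| Literal, all ten stay at 0 | 16/30 | 53.3% | 34.3–71.7% |
| Literal, eight of ten stay at 0 | 14/30 | 46.7% | 28.3–65.7% |
| Change required | 6/30 | 20.0% | 7.7–38.6% |

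**Second set, r = 40%, all baseline Grade 0 subjects staying at 0.**

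| At Grade 0 at baseline | With the sign only (95% CI) | Literal | Change required |
|---|---|---|---|
| 5 | 10/25 = 40% (21.1–61.3%) | 15/30 = 50% | 10/30 = 33% |
| 10 | 8/20 = 40% (19.1–63.9%) | 18/30 = 60% | 8/30 = 27% |
| 15 | 6/15 = 40% (16.3–67.7%) | 21/30 = 70% | 6/30 = 20% |

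The restricted rate stays at r. The other two move in opposite directions as the number without the sign grows, although nothing about response has changed.

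**Eye rule.** The text does not say whether the worse eye is chosen separately for each sign. If one eye is chosen overall, it may be at Grade 0 on flare while the other eye has flare. Choosing per sign removes that case, but not the subject at Grade 0 in both eyes.

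**The case against.** The strongest points on the other side are these.

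- **The direction is unknown.** The Grade 0 clause is a parenthesis attached to a reduction from baseline, and may exist only to credit subjects whose starting grade is too low for a two-step fall. A subject at 0 throughout would then be a non-responder, and the error would be understatement. This is a fair reading, but it does not rescue the rate, because subjects who cannot respond stay in the denominator.
- **A rate over all treated subjects is a legitimate target, and staying at 0 during the taper of background therapy is informative.** Both are true. But maintaining absence is a different outcome from the reduction named in the objective, and the two should not be pooled in one figure.
- **The eye rule probably works endpoint by endpoint.** The sentence extending the principle to other change-from-baseline endpoints leans that way, which would make a Grade 0 baseline less likely. It is not explicit, and it does not help when both eyes are at 0.
- **The size is assumed and may be trivial.** This stands: the documents give no baseline grades.
- **A cut-off above 0 is only a partial cure.** A subject at the lowest non-zero grade still responds by a single step to 0. This stands, but it follows from the endpoint's own definition and is a separate matter.
- **This is an exploratory pilot with nominal p-values, and only the Synopsis is available.** No error-rate claim depends on the point, and fuller definitions elsewhere cannot be ruled out. The Synopsis nevertheless states endpoints, analysis sets and eye rule, and is silent on this case.

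**Conclusion.** The concern holds and should be corrected before any endpoint is scored. Under the plan as written, each primary rate depends on how many subjects lacked the sign at entry and on a scoring choice the text does not make. Neither reading estimates reduction among subjects who have the sign.

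The size rests wholly on assumed z, s and r. With r = 30% and 20% to 50% of subjects at Grade 0 at baseline, the reported rate runs from 36% to 65% on the literal reading (s from 60% to 100%) and from 24% down to 15% if a change is required. At z = 5% it stays between 28.5% and 33.5%. The structural finding does not depend on these values: it follows from the entry rule, the endpoint wording and the analysis sets. It affects interpretation of the rates and their intervals, not a stated power or error rate.

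**What to change.** For each of the three endpoints:

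1. State that the analysed eye is the worse eye on that sign, keeping the existing right-eye rule for ties.
2. Restrict the responder denominator, in both mITT and Per-Protocol, to subjects with a baseline grade above 0 on that sign in that eye.
3. Count Grade 0 at week 36 as response only from a non-zero baseline.
4. Report the evaluable number beside the rate and its 95% CI.
5. Report baseline Grade 0 subjects separately, as stayed at 0 or worsened.

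If a rate over all mITT subjects is kept, label it supportive and state how baseline Grade 0 is scored.

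**Cost.** Only the endpoint, eye-rule and analysis-set wording changes; no new data are needed. Intervals widen: in the worked case the denominator falls from 30 to 20, and the width is 54.3 − 11.9 = 42.4 points, against 71.7 − 34.3 = 37.4 (literal, all ten staying at 0) or 38.6 − 7.7 = 30.9 (change required). Subjects who enter on a lesion alone with Grade 0 on all three signs leave every primary denominator, which is right for a reduction endpoint but should be stated openly in a study of this size. Each endpoint then rests on a different subset, so the three rates should not be compared with one another.

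### Mean change is the only IOP endpoint visible in the synopsis; with about 30 subjects it is insensitive to large rises in a few, so a prespecified count should stand beside it

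*Combined protocol and SAP*

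**What the plan says.** In section 6 (Synopsis), the secondary objective concerns safety and tolerability, and four endpoints serve it. Two are adverse event (AE) endpoints, one ocular ("Incidence and severity of ocular adverse events (AEs") and one for all other AEs. The third is "New or worsening cataracts". The fourth, and the only one on pressure, is "Mean change in intra-ocular pressure (IOP". No eye, visit, threshold or largest-rise summary is attached to it.

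Under Safety Analysis, treatment-emergent and serious AEs are tabulated by MedDRA term. For the rest: "Other safety data will be listed and summarized descriptively or graphically, as appropriate".

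Under Efficacy Analysis, when both eyes are affected, the eye that was worse at baseline is used, with the right eye on ties. That rule is then extended: "The same principle will be applied to efficacy endpoints when change from baseline is evaluated". Nothing visible applies it to a safety endpoint such as IOP.

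On size: "A total of 30 subjects will be enrolled in this study", and "No formal sample size calculations were performed". On who is analysed: "The Safety Population will include all subjects who receive 1 or more doses of study drug".

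**The concern.** A pressure rise is a harm to an individual subject, often to one eye. A mean change describes the group. With 30 subjects, each contributes one thirtieth of the mean, so large rises in two or three move it only slightly, and small falls in the others can cancel them. A report that relied on this endpoint could describe little or no IOP change while a material fraction of subjects had large rises. That would serve the safety objective poorly, although finding individual harm is something a 30-subject single-arm study can usefully do.

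The missing eye and time point add to this. The mean could be formed in several ways, and the visible text does not say which.

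**Working it through.** The plan contains no IOP calculation to reproduce: no SD, expected change or threshold is given. The check is therefore an illustration. Only n = 30 comes from the documents. The number of affected subjects, the size of the rise, the SD and the average change in the others are assumptions.

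**Step 1. Mean and 95% CI with 3 affected subjects, each rising 12 mmHg.** Let the other 27 have mean change m and SD s.

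- Mean = (3 × 12 + 27 × m)/30.
- Total sum of squares = 3 × (12 - mean)² + 27 × (m - mean)² + 26 × s².
- SD of change = √(sum of squares/29).
- CI = mean ± 2.045 × SD/√30 (t with 29 df).

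| m | s | Mean | Sum of squares | SD | 95% CI |
|---|---|---|---|---|---|
| 0 | 0 | 36/30 = +1.2 | 349.92 + 38.88 = 388.8 | 3.66 | -0.17 to 2.57 |
| 0 | 4 | +1.2 | 388.8 + 416 = 804.8 | 5.27 | -0.77 to 3.17 |
| -1 | 3 | (36 - 27)/30 = +0.3 | 410.67 + 45.63 + 234 = 690.3 | 4.88 | -1.52 to 2.12 |

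**Step 2. Does this depend on the choice of 12 mmHg?** If k of n subjects rise by r and the rest do not change, r cancels from the one-sample t statistic: t = √((n - 1) × p/(1 - p)), with p = k/n.

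- k = 1: √(29 × 1/29) = 1.00
- k = 2: √(29 × 2/28) = 1.44
- k = 3: √(29 × 0.1/0.9) = 1.795
- k = 4: √(29 × 4/26) = 2.11

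The critical value is 2.045. With up to 3 affected subjects and no other variation, the CI includes zero however large the rise. With 4 it no longer does.

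**Step 3. Adding noise.** In simulation (40,000 trials per scenario; 3 of 30 rising by 10, 15 or 20 mmHg; SD 2 to 5 mmHg):

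- If the others average no change, the mean is about +1.0, +1.5 or +2.0 mmHg, and p < 0.05 occurs in 11% to 18% of trials.
- If the others fall by 1 mmHg on average, the mean is about +0.1, +0.6 or +1.1 mmHg, and p < 0.05 occurs in about 2% of trials or fewer.
- A mean of exactly zero needs an average fall of r/9 in the others, that is 1.1 to 2.2 mmHg.

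**Step 4. The same data as a count.** 3/30 = 10%. The Clopper-Pearson limits are the 2.5% point of Beta(3, 28) and the 97.5% point of Beta(4, 27): 2.1% to 26.5%. If the true rate is 10%, the chance of seeing at least one case is 1 - 0.9³⁰ = 95.8%. With 0/30, the upper limit is 11.6%.

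**The case against.** The strongest reply is that the plan does not rely on the mean alone. Ocular AEs and cataracts are also secondary endpoints, and a large pressure rise could be reported as an ocular AE. Ophthalmology examinations are a named safety assessment. Listings would show individual values, and a routine descriptive table includes the SD and maximum. In the scenarios above the SD is 3.7 to 5.3 mmHg and the largest rise at least 12 mmHg, which would not look null to a careful reader. The visible text names no IOP test or decision rule, so a CI that spans zero decides nothing. The study is also an exploratory pilot.

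Most of this stands and limits the point. What remains is that neither route is a count against a cut-off fixed before the data are seen, and the visible text does not say which IOP values would have to be reported as AEs.

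Stronger readings are tempting, but the documents do not support them:

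- *That mean IOP is the trial's main ocular safety measure.* It is one of four secondary endpoints, and nothing ranks it first.
- *That IOP will be averaged over visits or eyes, or limited to the efficacy eye.* No text says so; the eye and visit are simply not stated.
- *That AE reporting will miss pressure rises because investigators are unmasked.* The study is open label, but no AE definition or rule for abnormal measurements is visible.
- *That the plan has no categorical IOP analysis.* The exploratory endpoints are redacted and only the synopsis is available, so one may exist elsewhere.

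**Conclusion.** The point holds as a gap in the sensitivity of the visible endpoint list. Under the stated assumptions, 3 of 30 subjects with a 12 mmHg rise appear as a mean change of +1.2 mmHg with a CI that includes zero, or as about +0.3 mmHg if the others fall by 1 mmHg on average. A count shows the same data as 10% of subjects. That up to 3 of 30 affected subjects leave the CI spanning zero does not depend on the size of the rise, provided the others do not change. A near-zero mean, as opposed to a small positive one, needs an offsetting fall in the others.

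Nothing in the plan is contradictory. This is a worthwhile, inexpensive improvement to a pilot's safety reporting, and it would be met already if an equivalent analysis sits in text that is not available here.

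**What to change.** Keep mean change in IOP and state the eye and visit it refers to. Beside it, add to the secondary safety endpoints the number and percentage of subjects, with exact 95% CI, who exceed a prespecified IOP reporting threshold in either eye at any postbaseline visit. Define the threshold both as a change from baseline and as an absolute value. The sponsor's ophthalmology lead should set the cut-offs before data review; they classify results for reporting and are not treatment triggers. Also tabulate subjects who start or increase IOP-lowering medication, using the concomitant medication records that the plan already requires throughout the study. If a categorical IOP analysis exists in redacted or unavailable sections, list it with the secondary endpoints instead.

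The cost is a short addition to the endpoint list, agreement on cut-offs in advance, and one extra table. This assumes that IOP is recorded for each eye at the examination visits; no visit schedule is visible to confirm it. The safety profile may also look less favourable than the mean alone would suggest.

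### The synopsis defines the three primary responses by week-36 grade alone, so a subject who meets the grade after uveitis treatment was added or raised above baseline counts as an mITT responder

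*Combined protocol and SAP*

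**What the plan says.** All references are to section 6, Synopsis, which is the only text available.

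- **Primary endpoints (Objectives; Efficacy Analysis).** The first is "Proportion of subjects with a 2 or more step reduction from baseline (or achievement of Grade 0) in vitreous haze at 36 weeks". Aqueous flare and aqueous cells use the same form. None of the three mentions other treatment, and this wording is not redacted.
- **Evaluated eye (Efficacy Analysis).** When both eyes are affected, "the change from baseline will be determined based on the eye with the worst severity at baseline"; the right eye is used if they are equal.
- **Uveitis treatment (Concomitant Medications and Treatments).** One sentence covers corticosteroids as well: "immunomodulators for uveitis are permitted provided the subject has been on a stable dose for at least 2 weeks prior to the Screening Visit". A second condition in it is that the person "is willing to taper to the lowest effective dose during the study". The entry criteria also require willingness to taper.
- **Local corticosteroid (same section).** The prohibition covers "topical, ophthalmic, or intra-ocular corticosteroids for a concomitant condition during the study". It does not name local corticosteroid given for the uveitis itself.
- **Recording (same section).** All medications are recorded from 30 days before Screening to the end of the study.
- **Populations (Analysis Populations).** mITT is "all subjects who receive at least 1 dose of study drug and who contribute any postbaseline efficacy data to the study". Per-Protocol is the mITT subset who "complete the study as per protocol, have no missing primary endpoint data, and do not have any major protocol deviations".
- **Use of the populations (Efficacy Analysis).** "The primary efficacy endpoints will be analyzed on both mITT population and the Per-Protocol population".

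**The concern.** Subjects enter with active disease despite oral corticosteroid, and are then expected to reduce their background treatment over a 36-week period. A flare that leads to more treatment is a foreseeable event, although the documents give no frequency for it. If the eye then improves by two grades, or reaches Grade 0, the endpoint as worded records a response.

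The primary objective is to explore what Acthar does to aqueous and vitreous inflammation. The study is open label and no control arm is described, so nothing in the design separates Acthar's contribution from that of the added drug. Compared with a rule that counts such subjects as failures, grade-only scoring can raise the response rate or leave it unchanged, but cannot lower it. The three response rates are the main output of the study, and a reader would not know whether they describe Acthar with background treatment at or below baseline, or Acthar plus whatever else was needed.

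**Working it through.** There is no figure in the plan to reproduce. The sample size of 30 is empirical, and the supplied text gives no expected response rate or null proportion. The check is therefore a reading of the definitions, followed by an illustration.

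**Step 1: trace one subject through the definitions.** Suppose a subject is dosed, has postbaseline efficacy data, starts a new uveitis agent before week 36, and meets the grade criterion at week 36.

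- *mITT membership:* yes. It needs one dose and any postbaseline efficacy data, and has no exclusion for deviations.
- *Response:* yes. Only the grade is consulted.
- *Effect of the concomitant-treatment section:* starting the agent may be a deviation. Nothing in the supplied text turns a deviation into a non-response.
- *Per-Protocol membership:* possibly no, by either of two routes: not completing the study as per protocol, or having a major deviation. If excluded, the subject leaves both numerator and denominator.

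**Step 2: size per subject.** Take n = 30, assuming all enrolled subjects enter mITT. If k responders had added treatment, the rate moves by k/n:

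- 1/30 = 3.3 points
- 2/30 = 6.7 points
- 3/30 = 10.0 points
- 4/30 = 13.3 points

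**Step 3: illustration (all counts assumed).** Twelve of 30 meet the grade criterion. Four subjects had treatment added or raised above baseline; two of them are among the 12. Intervals are exact (Clopper-Pearson) 95%.

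| Scoring | Calculation | Rate | 95% CI |
|---|---|---|---|
| Grade only, mITT (as written) | 12/30 | 40.0% | 22.7 to 59.4 |
| Added treatment = non-response, mITT | (12 − 2)/30 = 10/30 | 33.3% | 17.3 to 52.8 |
| Per-Protocol, these four the only exclusions | (12 − 2)/(30 − 4) = 10/26 | 38.5% | 20.2 to 59.4 |

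**Step 4: does the Per-Protocol comparison depend on the two-and-two split?** Let a of the four be grade responders. Per-Protocol gives (12 − a)/26 and the non-response rule gives (12 − a)/30.

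| a | Per-Protocol | Non-response rule |
|---|---|---|
| 0 | 12/26 = 46.2% | 12/30 = 40.0% |
| 1 | 11/26 = 42.3% | 11/30 = 36.7% |
| 2 | 10/26 = 38.5% | 10/30 = 33.3% |
| 3 | 9/26 = 34.6% | 9/30 = 30.0% |
| 4 | 8/26 = 30.8% | 8/30 = 26.7% |

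How close Per-Protocol comes to the grade-only 40.0% does depend on the split. That it lies above the non-response rule does not: the numerator is the same and the denominator is smaller. Per-Protocol therefore answers a different question and does not replace the scoring rule.

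**The case against.** **This is silence in a summary.** A synopsis need not carry rules for treatment failure, and one may exist in the protocol body or a separate SAP. This stands as a limit. A reader might infer that the trial has no such rule anywhere; the available text cannot support that. It does show that the endpoint wording in the synopsis carries none.

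**The plan may already forbid the event.** The permission rests on a stable dose and willingness to taper, and the only change described is downward. It covers corticosteroid for uveitis without limiting the route, so it can be read as excluding increases and newly started local corticosteroid as well as new agents. This stands. A reader might infer from the wording of the local corticosteroid prohibition that local treatment for uveitis is freely allowed; the text does not establish that. Even on the stricter reading, however, the consequence is a deviation, and mITT scoring is unchanged.

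**Per-Protocol is a safeguard.** It is planned for all three endpoints, and exclusion does not depend only on a deviation being classed as major, because completing as per protocol is a separate condition. This stands in part: such subjects may be excluded, but they are never counted as failures.

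**Week-36 grade regardless of other treatment is a recognised target.** True (a treatment-policy approach), and re-scoring does not remove confounding from permitted background treatment or natural fluctuation. In a study with no described control arm, however, the grade-only rate cannot be read as Acthar's effect, so it serves better as the sensitivity analysis.

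**No decision is at stake.** A reader might infer that the binomial tests are invalid or a success claim is inflated. The documents do not support that: the supplied text gives no null proportion or success criterion, p-values are nominal, and the illustrated shift lies inside the confidence intervals.

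**Conclusion.** The point holds in limited form. As the synopsis is worded, meeting the grade at week 36 after uveitis treatment was added or raised above baseline is an mITT response, and this can bias the rate upward as a measure of Acthar's effect. Neither the concomitant-treatment conditions nor the Per-Protocol analysis corrects it.

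The size is unknown because the documents give no count of such subjects. Each is worth 3.3 points if all 30 enter mITT; the 40.0% against 33.3% comparison rests on assumed counts. The concern is the direction of bias and how the rates are read, in an exploratory pilot. It should be fixed, with medium confidence, since a rule outside the synopsis could not be checked.

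Stepping treatment back up to a level at or below baseline is not part of the concern. A reader might want to call every re-escalation a failure, but the plan asks subjects to find their lowest effective dose, and such movement belongs to that taper.

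**What to change.** This changes scoring only, not how any subject is treated. For the three primary endpoints in mITT, count as a non-responder any subject who, before the week-36 assessment:

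- (a) has systemic corticosteroid or immunomodulator for uveitis raised above the baseline dose;
- (b) starts a new agent for uveitis; or
- (c) has local ocular corticosteroid for uveitis newly started, or raised above baseline use, in the evaluated eye.

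Continuing, tapering, or stepping back up at or below baseline use is not failure; tabulate it. Report the grade-only rule as a sensitivity analysis, and show the number re-scored beside each rate. If the full protocol or SAP already contains such a rule, carry it into the synopsis endpoint wording.

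**Cost.** Endpoint and SAP wording. Medications are already recorded throughout; dose, dates, indication and, for local treatment, the eye treated are needed if not already captured. The reported rate may be lower, and a brief increase above baseline that is later tapered counts as failure. The grade-only sensitivity analysis shows how much the rule changes each rate.
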